## 16.3 Interim analyses and stop/go decisions

We will carry out interim analyses when 33% and 50% of participants reach the primary outcome. At 33% we will calculate the 95% confidence interval of the PPV of the test that included the expected 80% PPV, and excluded a PPV of 50% with 90% power. Were the CI to exclude 80%, and show not to be significantly different from 50%, the trial will stop due to poor accuracy of the biomarker test. At 50% we will validate the sensitivity of the test using data from the 37 participants randomized to arm A only (weaning all), which will allow us to estimate with 80% power the 95% confidence interval of the sensitivity that included 70% and excluded 50%.

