### 5.5 Trial Duration

Estimated recruitment period: 18 months.

Individual patient follow-up following enrolment: 48 months (6-12 months drug weaning, 36 months post-weaning follow-up).

Total estimated study duration: 72 months.

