#### 8.3 Immunosuppression Withdrawal Protocol (Arms A and B+)

# Weaning from calcineurin inhibitor (CNI) or mycophenolate/mycophenolic acid monotherapy:

- Participants will initiate IS weaning after at least 3 weeks of stable liver function (as documented by 2 separated laboratory exams).
- Weaning will occur in eight 3-week intervals with each subsequent reduction based on liver function test stability over the prior 3-week interval.
- No single reduction should exceed 50% of the daily dose except the final reduction.
   Withdrawal will proceed as follows:
  - Reduce total daily dose to 75% current total dose x 3 weeks
  - Reduce total daily dose to 75% current total dose x 3 weeks
  - Reduce total daily dose to 50-75% current total dose x 3 weeks
  - Give above dose 5x weekly x 3 weeks with consolidation to once daily dose
  - Give current dose 4x weekly x 3 weeks
  - Give current dose 3x weekly x 3 weeks
  - Give current dose 2x weekly x 3 weeks
  - Give current dose 1x weekly x 3 weeks and discontinue

Effective contraception must be used before beginning mycophenolate/mycophenolic acid therapy, during therapy, and for six weeks following discontinuation of therapy (please see Appendix 6 for details on acceptable forms of contraception).

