### - Pausing of IS weaning:

 In the case of adverse events that could compromise safety, IS withdrawal can be temporarily paused for up to 4 weeks. During this time interval the participant will remain at the current dose. Participants are allowed up to 3 non-consecutive pauses. IS withdrawal will also be temporarily paused during the investigation of allograft dysfunction.

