# 9. ENDPOINTS

#### 9.1 Primary endpoint

The primary endpoint is defined as the successful discontinuation of IS with maintainance of normal allograft status as assessed by liver biopsy and liver tests 12 and 24 months after IS withdrawal (operational tolerance) and stable liver tests (12, 24 and 36 months after IS withdrawal). For the purposes of validating the clinical usefulness of the tolerance biomarker, successful IS withdrawal is considered the Gold Standard. Since this outcome is strictly restricted to the IS withdrawal process and by definition cannot be observed in Arm B-, the analysis of the primary outcome will be restricted to Arms A and B+.

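### The interim looks wait for an outcome needing 36 months off drug, so the stop for poor biomarker accuracy falls about two years after the last planned weaning has ended

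*Protocol*

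**What the plan says.** Protocol section 16.3 states: "We will carry out interim analyses when 33% and 50% of participants reach the primary outcome". At the 33% look a 95% confidence interval for the positive predictive value (PPV) is formed. If it excludes 80% and the PPV does not differ significantly from 50%, "the trial will stop due to poor accuracy of the biomarker test". The 50% look concerns sensitivity, "using data from the 37 participants randomized to arm A only (weaning all").

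Section 9.1, like the synopsis, defines the primary outcome as discontinuation with satisfactory biopsies at 12 and 24 months and "stable liver tests (12, 24 and 36 months after IS withdrawal"). Section 5.5 gives "Estimated recruitment period: 18 months" and individual follow-up of "48 months (6-12 months drug weaning, 36 months post-weaning follow-up"). Section 8.3 sets the pace for monotherapy ("Weaning will occur in eight 3-week intervals"), adds further steps for a second drug, and says of pauses: "Participants are allowed up to 3 non-consecutive pauses".

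Success is described differently in two other places. Section 12.1 defines operational tolerance 12 months after discontinuation. The hypothesis in section 15 concerns participants who start withdrawal and finish it without rejection. Section 16.3 does not say which of these triggers a look, or which participants form the denominator.

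**The concern.** An accuracy stop is useful if it can act while participants are still to be weaned, or are being weaned, on the strength of the test. A success under section 9.1 cannot be known until about 42-48 months after randomisation, whereas recruitment is planned to close at month 18. If the looks wait for that outcome, everyone in Arms A and B+ will long since have attempted withdrawal when the PPV is first examined. The rule would then be unable to do the main thing it appears designed for.

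**Working it through.** **1. The plan's own figures.** Inputs from section 15: 50% against 80% success, 5% type I error, 90% power, 2:1 allocation. The unpooled normal formula gives Arm A = (1.960 + 1.282)² × (0.25 + 0.16/0.5) / 0.30² = 66.5 and B+ = 33.3, together 99.8 (stated: 100). Then 67 + 67 = 134, and 134 × 1.10 = 147.4, taken as 148. Arm A is 74, and half of that is the 37 quoted for the second look. For the first look, 33% of 148 is 48.8, so 49 participants, of whom about 25 are biomarker-positive. An exact binomial test with n = 25, 0.80 against 0.50, two-sided 5%, has power 0.891 (stated: 90%). Both looks are therefore consistent with fixed fractions of the randomised sample.

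**2. Weaning length (section 8.3).** Monotherapy: 8 × 3 = 24 weeks, 5.5 months. Two drugs: 24 + 3 + 9 = 36 weeks. With three 4-week pauses: 48 weeks, 11 months. This agrees closely with the 6-12 months in section 5.5.

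**3. Calendar time of each look.** Month of look = 18 × n/148 + weaning + time off drug. Even accrual is an assumption. The 49th participant enters at 18 × 49/148 = month 6.0 and the 74th at month 9.0. The last finishes weaning at 18 + 6 = 24 to 18 + 12 = 30.

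| Outcome used | First 49 | First 74 | Last weaning ends |
|---|---|---|---|
| Section 9.1, 36 months off drug | 48-54 | 51-57 | 24-30 |
| Section 12.1, 12 months off drug | 24-30 | 27-33 | 24-30 |
| Section 15, weaning completed | 12-18 | 15-21 | 24-30 |

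At equal weaning length the section 9.1 looks trail the last weaning by 36 − (18 − 6) = 24 and 36 − (18 − 9) = 27 months. Pairing the shortest weaning in the look cohort with the longest in the last participant still leaves 48 − 30 = 18 months.

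**4. Slower recruitment.** With recruitment of R months, the 33% look precedes the end of weaning only if 0.33R + 36 < R, so R > 36/0.67 = 54 months. For the 50% look, R > 36/0.50 = 72 months.

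**5. Secondary reading: a look is triggered by any known outcome.** Expected failures are 74 × 0.50 + 37 × 0.20 = 37 + 7.4 = 44.4. Section 4.1.2 says that most rejections come during or soon after weaning, while no success is known before about month 42. Had all failures become known first, the failure shares would be:

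- 37 known outcomes (33% of the 111 in A and B+): up to 100%; 99% by simulation.
- 49 known outcomes (33% of 148): 44.4/49 = 91%; 86-90% by simulation.
- 56 known outcomes (50% of 111): 44.4/56 = 79%; 77-79% by simulation.
- 74 known outcomes (50% of 148): 44.4/74 = 60%; 60% by simulation.

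The simulation assumed even accrual, early failures spread up to 6 months after weaning, and 0-40% of failures found at the 12- or 24-month biopsy.

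**6. Timing under the fix below.** Looks at 12 months after randomisation fall at 6 + 12 = month 18 and 9 + 12 = month 21. At month 18 the share of weaning-arm participants still weaning is 6/18, 9/18 or 12/18 for weaning of 6, 9 or 12 months, before removing those who have already failed.

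**The case against.** A reader might infer that the first look would consist almost entirely of failures, so that a good biomarker would look useless. On the known-outcome reading, with a true PPV of 0.80, a simulated interim PPV is below 1% at 37 known outcomes and about 22% at 49. The documents do not support making this the main point. The 37 Arm A participants in section 16.3 are half of those randomised to that arm, and the 90% power at the first look reproduces with 25 biomarker-positive participants. Both suggest a cohort fixed by randomisation. The simulated values also rest on assumed failure times, and the 50% look would be 60-79% failures, not nearly all. What remains is that the wording does not exclude this reading, under which early failures would dominate the 33% look and bias the PPV downward.

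It can also be said that section 9.1 is not the only definition. On the section 15 wording the looks do precede the end of weaning. That is true, but section 16.3 refers to the primary outcome, which section 9.1 defines, and the 12-month definition does not rescue the timing.

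Accrual may have run longer than planned: the amendment log shows sites added in 2017 and 2018, after a first amendment submitted in March 2015. This narrows the gap but is not shown to reach the 54 months needed.

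Finally, this is an accuracy stop and not the safety safeguard. Sections 14 and 18.2 provide separate triggers for death, graft loss and severe rejection, with three-monthly committee meetings. A late stop could also still save some follow-up and some of the Arm B- biopsies due 48 months after enrolment, up to month 18 + 48 = 66. All of this stands and lowers the severity.

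**Conclusion.** The point holds for timing. Read with section 9.1, the looks in section 16.3 fall at about months 48-54 and 51-57, roughly two years after the last planned weaning ends at month 24-30. The stop for poor accuracy therefore cannot spare any participant a withdrawal attempt. The section 12.1 definition gives months 24-33, at about or after the end of weaning; only the section 15 wording gives useful looks, at months 12-21. The result assumes even accrual over the planned 18 months and weaning of 6-12 months, and for the first look it survives any recruitment period up to about 54 months. The bias from early failures is a secondary risk of loose wording, not an established defect. It would go too far to infer that participants lack safety oversight or that the final primary analysis is wrong; neither is shown. This should be fixed, but it does not undermine the trial.

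**What to change.** Reword section 16.3 as follows:

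- Fix each look by randomisation order: the first 49 randomised, then the first 74. This keeps the plan's figures of about 25 biomarker-positive participants and 37 in Arm A.
- Analyse each set when all its members have reached 12 months after randomisation.
- Define interim failure as rejection or failure to complete weaning by then. Do not count rejection-free participants whose weaning is still in progress as failures. Without this proviso, a participant on a long, paused course could be scored a failure and later meet the endpoint.
- State that this is an interim outcome, distinct from the primary one, and reconcile the descriptions of success in sections 9.1, 12.1, 15 and 16.3.

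Because anyone who fails on the interim outcome also fails on the primary one, the interim PPV is an upper bound for the primary-outcome PPV in the same cohort, and a stop based on it is conservative. This argument covers the PPV only, not the sensitivity estimated at the second look.

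The cost is amendment wording and a matching change to the monitoring committee's charter; the data are already collected. There are two drawbacks. The early outcome overstates the final PPV, so some poor tests will pass. And the first look falls at about month 18, when recruitment is ending, so it can matter only for those still weaning: at most about two-thirds, more likely one-third to one-half.

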
[figure not shown]
Taken together, these results indicate that when liver transplant recipients are carefully selected according to clinical and histological criteria (e.g. >3 years after transplantation, absence of recent episodes of rejection, no autoimmunity and liver biopsy without significant inflammatory damage), and drug withdrawal is carefully performed following well standardized protocols, tolerance is observed in approximately 15-40% of recipients, and even more in very long-term surviving patients. This makes IS withdrawal a tangible clinical opportunity in the setting of liver transplantation. Consideration of IS withdrawal, however, must carefully weigh the risks of inciting graft rejection. There is a need therefore for precise prospective identification of individuals who have become operationally tolerant to their transplanted liver. This would allow personalized medical patient care by safe drug elimination in select subjects and may also provide clues to the mechanisms accounting for tolerance generation, thereby facilitating the intentional induction of tolerance in those who do not develop it spontaneously.

Recent studies from [name]'s group suggest that liver operational tolerance can be predicted employing cellular and/or molecular biomarkers. A gene expression signature indicative of tolerance was first identified in blood from operationally tolerant recipients and appropriate controls. This signature included genes encoding gamma-deltaT cells and NK cells (15, 16). These findings were prospectively validated on samples collected before IS discontinuation in the RISET Consortium trial (17). Microarray and real-time PCR experiments conducted on peripheral blood mononuclear cells (PBMC) samples confirmed the over-representation of transcripts preferentially expressed by NK cells in tolerant patients. However, the PBMC molecular signature lacked reproducibility across the 3 participating clinical centres and could not reliably predict the outcome of IS withdrawal.

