### 5.4 Trial Design

This is a prospective, multi-centre, phase IV, biomarker-strategy design trial with a randomised control group in which adult liver transplant recipients will undergo IS withdrawal. Enrolled participants will be randomised 1:1 to either: 1) Non-Biomarker-based IS weaning (Weaning-All; Arm A); or 2) Biomarker-based IS weaning (Arm B). In participants allocated to Arm A IS will be withdrawn regardless of the result of the biomarker test. Among participants allocated to Arm B, only those found to be biomarker-positive (Arm B+, i.e. potentially tolerant) will be offered IS withdrawal, while biomarker-negative participants (Arm B-, i.e. potentially non-tolerant) will remain on their

baseline maintenance IS. This will allow us to demonstrate that the biomarker is a useful test to personalise IS by offering drug withdrawal only to those participants who are likely to complete the process successfully, avoiding unnecessary rejections among those who have not developed tolerance. Comparing the outcome of IS withdrawal between arms A and B+ will provide direct evidence of the clinical usefulness of the test as a function of its predictive accuracy. We have established that for the biomarker to drive safe IS withdrawal its Positive Predictive Value  $(PPV = \frac{Number Actually Tolerant}{Number Biomarker+})$  should be no less than 0.80, and its sensitivity at least 070. To account for centre effects, we will use stratified randomization. Furthermore, to avoid biases, participants undergoing drug withdrawal and their physicians will be blinded to the biomarker results. Participants randomized to Arm B- will know their biomarker status, and will be maintained in the study until they complete 48 months of follow-up post randomisation. They will contribute to secondary clinical outcomes and to the evaluation of the stability of the tolerance signature.

Cost and quality of life (HrQOL) assessments will be conducted alongside the trial to estimate the health-economic implications of the 2 different strategies. Furthermore, sequential biological specimens will be collected to conduct ancillary mechanistic studies. Recruitment will take place in 14 European liver transplant units (King's College Hospital, Royal Free London, Newcastle, Birmingham, Leeds, Edinburgh, Cambridge, Leuven, Hannover, Berlin, Barcelona, Dublin, Cliniques Universitaires Saint-Luc and Palermo-ISMETT).

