# 15. PROPOSED SAMPLE SIZE

#### Primary Hypothesis

To demonstrate the superiority of biomarker-led IS withdrawal over maintenance IS for hard clinical outcomes such as long term survival or incidence of IS-related side effects, the trial would require an unrealistically large sample size and a very lengthy follow-up. Notwithstanding, given the well known potential long-term benefits of IS withdrawal and the health-economic implications, the current study has been designed and powered to test the hypothesis that the IS weaning under the novel "Biomarker-based" strategy (Arm B+) is superior to Weaning All (Arm A), with respect to the proportion of participants who, having started the IS withdrawal protocol, complete it successfully without undergoing allograft rejection. Comparing arms A and B+ will show the utility of the biomarker as a clinical decision tool, as a function of its predictive accuracy. We have established that for the biomarker to drive safe IS withdrawal its Positive Predictive Value (*PPV* =  $\frac{Number Actually Tolerant}{Number Biomarker+}$ ) should be no less than 0.80, which would result into a statistically significant difference in the proportion of successfully weaned participants between arms A and B+. If the biomaker's PPV was 0.50, then participants in arm B+ would be no

better than taken at random, and there would be no difference with respect to arm A. Additionally, for the biomarker test to be considered successfully validated for clinical use, its sensitivity as estimated within arm A should be at least 0.70.

Expectations:

- **Biomarker Allocation:** Approximately 50% of participants will be positive for the biomarker (17).
- Arm A: 50% Successfully weaned participants vs.
- Arm B+: Under H0: 50% successfully weaned participants (if PPV = 0.50); under H1: 80% or more successfully weaned participants (if PPV ≥ 0.80).

100 participants would be sufficient to show superiority of Arm B+ compared to Arm A, with 90% power and 5% type I error rate, assuming an allocation ratio of 2:1 between arms A and B+ (given 50% biomarker positive). The resulting sample size including participants allocated to arm B- would be 134 subjects. To account for dropouts, the final sample size will be increased in 10%, resulting in a total of 148 participants.

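### The stop rule at the 33% interim is two-sided about 50%, so a PPV significantly below 50% does not trigger it

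*Protocol*

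**What the plan says.** Protocol section 16.3 plans two looks: "We will carry out interim analyses when 33% and 50% of participants reach the primary outcome". At the first, the plan calculates "the 95% confidence interval of the PPV of the test that included the expected 80% PPV, and excluded a PPV of 50% with 90% power". The decision rule follows: "Were the CI to exclude 80%, and show not to be significantly different from 50%, the trial will stop due to poor accuracy".

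Two other places fix what the reference values mean. Section 5.4 requires that the PPV "should be no less than 0.80, and its sensitivity at least 070". Section 15 treats a PPV of 0.50 as the value at which selection by biomarker is no better than chance, given 50% success in Arm A.

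On the background rate, section 4.1.1 says that with careful selection "tolerance is observed in approximately 15-40% of recipients", and adds that it is higher in very long-term survivors.

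Section 14 lets the sponsor and chief investigator stop for any justifiable reason, including a DMEC request. It also lists safety events that pause the study for DMEC review. None of these refers to the PPV.

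**The concern.** The rule joins two conditions with 'and', and the second carries no direction. Consider an interval wholly below 50%. It excludes 80%, so the first condition is met. It also excludes 50%, so the PPV is significantly different from 50% and the second condition fails. The rule then calls for no stop.

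The rule is therefore not monotone: a middling result stops the trial and a worse one does not. Since the plan takes 0.50 as the no-value point and needs at least 0.80, a PPV below 0.50 is the strongest evidence of poor accuracy that the look could produce. What is at stake is whether a pre-specified futility rule gives an answer in that case or leaves it to discretion.

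**Working it through.** **Inputs**

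- Total sample size, section 15: "resulting in a total of 148 participants".
- Biomarker-positive share, section 15: about 50%.
- Section 16.3: 95% interval, reference PPVs 0.80 and 0.50, power 90%, look at 33%.

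**Interim denominator (an assumption; the protocol does not give it).** 0.33 × 148 = 48.8 participants, and half of these is 24.4, so 24 to 25 biomarker-positive participants if both arms are pooled. Counting Arm B+ only gives about 12.

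**Reproducing the plan's 90% power.** The normal approximation for excluding 0.50 when the true PPV is 0.80 is

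n = [(1.960 × √(0.5 × 0.5) + 1.282 × √(0.8 × 0.2)) / 0.30]² = [(0.980 + 0.513) / 0.30]² ≈ 24.75, so 25.

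At n = 25 the exact (Clopper-Pearson) lower limit first exceeds 0.50 at 18 successes, and P(X ≥ 18 | 25, 0.80) = 0.891. The stated 90% is reproduced, which supports n of about 25.

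**What the rule does at n = 25 (exact 95% intervals)**

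| Successes | Interval at the edges | Rule as written |
|---|---|---|
| 0–7 | 7/25: 0.121–0.494 | no stop (wholly below 0.50) |
| 8–15 | 8/25: 0.149–0.535; 15/25: 0.387–0.789 | stop |
| 16–17 | 16/25: upper limit 0.820 | no stop (contains both 0.50 and 0.80) |
| 18–25 | 18/25: lower limit 0.506 | no stop (excludes 0.50, not below 0.80) |

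So 15/25 (60%) stops the trial and 7/25 (28%) does not. Wilson and Wald intervals give the same 0–7 gap.

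**How often the gap is hit, and the effect of a one-sided second condition.** The gap is P(X ≤ 7), the stop as written is P(8 ≤ X ≤ 15), and the stop with the one-sided wording is P(X ≤ 15), all binomial with n = 25.

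| True PPV | Gap | Stop, as written | Stop, one-sided |
|---|---|---|---|
| 0.15 | 0.97 | 0.03 | 1.00 |
| 0.20 | 0.89 | 0.11 | 1.00 |
| 0.30 | 0.51 | 0.49 | 1.00 |
| 0.40 | 0.15 | 0.83 | 0.99 |
| 0.50 | 0.02 | 0.86 | 0.89 |
| 0.80 | 0.00 | 0.017 | 0.017 |

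**Sensitivity to the denominator.** With Arm B+ only (n = 12, exact intervals) the gap is 0–2 successes: P(X ≤ 2) = 0.02 at a PPV of 0.50, 0.25 at 0.30 and 0.56 at 0.20. The gap is smaller but still there.

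**Which PPVs are plausible.** A test with no information has a PPV equal to the background success rate, which section 4.1.1 puts at about 15–40%. That section also reports 42 of 102 (41%) in the adult European trial, with 30% in recipients under 6 years post-transplant and older than 50, 38% at 6–11 years, and 79% beyond 11 years.

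**The case against.** **The intent is plain.** The sentence speaks of poor accuracy, so a reader would take it to mean not better than 50%. That is probably right, and it makes this a drafting error. But the rule is stated in the protocol, and applied as written it gives the wrong answer.

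**The gap is rare in the plan's own no-value case.** This stands. At a PPV of 0.50 the gap is hit 2% of the time, and the rule stops in 86% of cases against 89% when corrected. The 97% at 0.15 and 89% at 0.20 need a PPV below every eligible subgroup rate quoted above, since inclusion criterion 1 removes younger recipients under 6 years post-transplant, who belong to the group with success below 15%. The recalibrated test had a PPV of 82% (section 4.1.1), and section 15 assumes 50% success in Arm A. The range of most interest for an uninformative test is 0.30–0.40, where the gap is 51% to 15%.

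**The rule does not oblige the trial to continue.** This also stands. It gives a condition for stopping and is silent otherwise. Under section 18.2 an independent DMEC that includes a biostatistician meets every 3 months.

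**A reader might infer that participants would go on being withdrawn on a test known to be poor.** The timetable does not support this. Section 9.1 requires stable liver tests 36 months after withdrawal. With weaning of 6–12 months, a success is confirmed 42–48 months after randomisation. Recruitment lasts 18 months, so weaning should end by about month 18 + 12 = 30. A look defined by participants completing that outcome falls after weaning is over. If failures count as having reached the outcome when they occur, the look comes earlier, but failures are then over-represented and the simple binomial table no longer applies.

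**A reader might also infer that the second condition does no useful work and should be deleted.** At n of about 25 no interval lies wholly between 0.50 and 0.80, so there it protects nothing. At larger looks it does: the Wilson interval for 24/36 is 0.503–0.798, and exact intervals between the two values appear from n = 44. Deletion would then stop a test whose PPV is significantly above 50%.

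**Conclusion.** The point holds as an error in a stated decision rule. As written, the 33% rule calls for no stop when the PPV is significantly below 50%, and no other pre-specified rule is tied to a low PPV. At about 25 biomarker-positive participants the gap is 0–7 successes.

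Its size depends on the true PPV: negligible at 0.50 (2%), modest at 0.40 (15%), and substantial at 0.30 (51%) and 0.20 (89%). These figures assume that the PPV is pooled over biomarker-positive participants in both arms, that 33% is taken of 148, that half are positive, and that outcomes at the look are a simple binomial sample. The existence of the gap does not depend on the assumed 25: it follows from the wording and remains at n = 12.

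The documents do not support saying that the trial must continue or that withdrawals would carry on because of this wording.

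**What to change.** In section 16.3, replace 'different from' with 'greater than' in the second condition. In terms of limits: stop for poor accuracy if the upper 95% limit of the PPV is below 0.80 and the lower limit is not above 0.50. State in the same sentence which participants form the denominator.

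At n = 25 the stop region becomes 0–15 successes instead of 8–15. The stop probability rises from 0.49 to 1.00 at a PPV of 0.30 and from 0.83 to 0.99 at 0.40. At a PPV of 0.80 the false-stop probability is unchanged at 1.7%. The cost is a change of wording in one section: no change to sample size, look timing or power.

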#### 8.2.2 Randomisation method

Randomisation will be via a 24 hour bespoke web based randomisation system hosted at the KCTU on a secure server. 148 adult liver transplant recipients will be randomised 1:1 at the level of the individual using the method of minimisation, stratified by site (11) and by the result of the Biomarker Test. The use of a random component in the minimisation algorithm will ensure that treatment allocation does not become deterministic and thus will protect pre-randomisation allocation concealment.

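### The 80% power for the interim sensitivity check counts all 37 Arm A participants, but only the 18 or 19 expected to be tolerant inform sensitivity; for the stated 95% interval it is about 33–48%

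*Protocol*

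**What the plan says.** Section 16.3 sets two looks: "We will carry out interim analyses when 33% and 50% of participants reach the primary outcome". The second look concerns sensitivity and is described as "using data from the 37 participants randomized to arm A only (weaning all), which will allow us to estimate with 80% power". The precision target attached to that power is a two-limit 95% interval for sensitivity containing 0.70 but not 0.50.

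Three other sections fix what this means:

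- Section 8.2.2: "148 adult liver transplant recipients will be randomised 1:1", so Arm A has 74 participants. The 37 is half of that and includes tolerant and non-tolerant participants alike.
- Section 9.1 makes successful withdrawal the reference standard against which the biomarker is judged.
- Section 15 plans on "Arm A: 50% Successfully weaned participants".

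Section 16.1 applies the same sensitivity criterion (interval includes 0.70, excludes 0.50) as a final condition for validating the biomarker. It gives no power for it.

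**The concern.** Participants who fail withdrawal inform specificity and predictive value, but they do not enter the denominator of sensitivity. A power figure based on all 37 therefore credits the look with about twice the information it will have. Nothing in the protocol restricts the 37 to tolerant participants.

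The look sits under a heading about stop/go decisions, and the text says it will validate the test. A monitoring committee told that the check has 80% power would read a failure to exclude 0.50 as evidence against the biomarker. With 18 or 19 tolerant participants, such a failure is more likely than not, or close to even odds, when the true sensitivity is exactly the 0.70 the protocol asks for.

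**Working it through.** **Inputs.** True sensitivity p1 = 0.70, value to exclude p0 = 0.50, 95% interval (section 16.3). Arm A at the look: 148 / 2 / 2 = 37 (sections 8.2.2 and 16.3). Tolerant share 50% (section 15), so 37 × 0.5 = 18.5 expected tolerant.

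**Formula.** One-sample normal approximation:

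power = Φ{ [p1 − p0 − z·√(p0(1 − p0)/n)] / √(p1(1 − p1)/n) }

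**Step 1: reproduce the 80%.** With n = 37, √(0.25/37) = 0.0822 and √(0.21/37) = 0.0753.

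- One-sided 5%: (0.20 − 1.645 × 0.0822)/0.0753 = 0.860, power 80.5% (exact binomial 80.7%). The n required for 80% is [(1.645 × 0.5 + 0.842 × 0.458)/0.20]² = 36.5, rounded up to 37.
- Two-sided 5%, which matches a 95% interval: (0.20 − 1.96 × 0.0822)/0.0753 = 0.516, power 69.7% (exact 69.8%). The n required for 80% is about 47.

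So the 80% needs both 37 tolerant participants and a one-sided 5% level.

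**Step 2: correct the denominator only** (one-sided 5% kept). The normal approximation gives 52.3% at n = 18 and 54.3% at n = 19; exact gives 53.4% and 47.4%. This step alone takes 80% to about 50%.

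**Step 3: also use the stated two-sided 95% interval.** Probability that the lower limit exceeds 0.50 when sensitivity is 0.70:

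| Tolerant in Arm A | Exact | Wilson | Wald |
|---|---|---|---|
| 18 | 33.3% | 33.3% | 53.4% |
| 19 | 28.2% | 47.4% | 47.4% |
| Random, Binomial(37, 0.50) | 32.9% | 41.9% | 47.7% |

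The averaged row is the one to use, because the tolerant count is not fixed and power at a single n jumps with the discreteness of the binomial. Requiring the interval also to include 0.70 lowers that row to 31.8%, 40.1% and 41.6%.

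**What this means at the look.** With 18 tolerant, the exact and Wilson intervals need at least 14 biomarker-positive. An observed 13/18 (72%, above target) has a lower limit of 0.465 (exact) or 0.491 (Wilson) and would not exclude 0.50.

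**Scenario with fewer tolerant.** The re-calibrated performance in section 4.1.1 (SN 72%, SP 89%, PPV 82%) implies a tolerant share of 0.82 × 0.11 / (0.72 × 0.18 + 0.82 × 0.11) = 0.41. Averaged over Binomial(37, 0.41), power is 26% (exact), 34% (Wilson) or 44% (Wald).

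**Contrast within section 16.3.** The 90% power for PPV at the 33% look does reproduce on the relevant subset: 148 × 0.33 ≈ 49 participants, about 25 of them biomarker-positive, 0.80 against 0.50, two-sided, gives 90.3%.

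**Final condition, for reference.** Averaged over Binomial(74, 0.50), power is 64% (exact) or 70% (Wilson). If about 67 in Arm A are evaluable (134 / 2, the size before the dropout allowance), it is 58% or 66%.

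**The case against.** No standard interval method brings 18 or 19 tolerant participants near 80%, so the core cannot be rebutted. Four limits on the point do stand.

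- A reader might infer that the denominator explains the whole drop. It does not: it takes 80% to about 50%, and the rest comes from pairing a one-sided calculation with a two-sided 95% interval.
- A reader might quote 26% as the true power. That figure replaces the planned 50% success rate with 41%, back-calculated from the re-calibration samples. It is a scenario, not a planning assumption of this trial.
- A reader might infer that a miss would stop the trial. Section 16.3 attaches its stopping rule to the PPV look only; no consequence is stated for the sensitivity look. The Arm A versus Arm B+ comparison and the total of 148 do not depend on it.
- A reader might say that the final sensitivity condition is also claimed at 80%. Section 16.1 states no power for it, so there is no figure there to correct.

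The protocol does not name an interval method in section 16.3. That detail can be left to an analysis plan, and it is why the corrected power is given as a range. An analysis plan cannot make the sentence itself true, because the sample, the power and the interval level it states do not fit together.

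**Conclusion.** The point holds for the interim figure. Section 16.3 states 80% power; on the protocol's own assumptions (50% tolerant in Arm A, true sensitivity 0.70, two-sided 95% interval excluding 0.50) it is about 33% (exact), 42% (Wilson) or 48% (Wald). At 41% tolerant it would be about 26–44%. The calculation assumes that all 37 have a known outcome and that the tolerant count varies binomially.

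The harm is a misleading validation verdict at mid-trial. Should-fix.

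**What to change.** In section 16.3:

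1. State that the interim sensitivity estimate rests on the tolerant participants in Arm A, expected to be 18 or 19 of the 37.
2. Replace 80% with about 33–48% and name the interval method that fixes the figure within that range.
3. Call the interim sensitivity estimate descriptive, and refer validation to the final condition already in section 16.1.

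If a power is added for that final condition, base it on the expected tolerant count: about 64–70% (exact/Wilson) with 74 in Arm A, or about 58–66% with about 67 evaluable.

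The cost is protocol wording and one less favourable figure. Sample size, visits and data collection are unchanged.
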